Participants will assess the severity of 7 influenza-associated symptoms (cough, sore throat, headache, nasal congestion, feverishness/chills, muscle/joint pain, and fatigue) on a 4-point scale (0 = no symptoms, 1= mild, 2 = moderate, and 3 = severe) as specified in section 4.5.7. Improvement is defined as: improvement pre-existing symptoms (i.e cough, fatigue, or muscle/join pain that existed prior to influenza) that were worse at baseline and improve at least 1 point from baseline; pre-existing symptoms not worse at baseline that maintain baseline severity; and new symptoms that are alleviated, defined as a symptom score of non (0) or mild (1).

Once all patient's influenza symptoms are alleviated, maintained, or improved (hereafter all will be called 'improvement') as defined above, the endpoint will be reached.

6. **Percentage of patients who experience each influenza-related complication** (hospitalization, death, sinusitis, otitis media, bronchitis, and radiologically-confirmed pneumonia) as an adverse event after the initiation of study treatment symptoms [symptoms [Time Frame: From Day 1 pre-treatment up to Day 30].
7. **Time to Return to Preinfluenza Health Status** [Time Frame: From Day 1 pre-treatment up to Day 30]. Participants will be asked to record their preinfluenza health status on a scale from 0 (worst possible health) to 10 (normal health [for someone same age and condition]), and their health status at baseline and every day after initiation of study treatment on the same scale as specified in section 4.5.7. Return to preinfluenza health status is defined as time from the initiation of the study treatment to the first time when the health status score was equal to or higher than the preinfluenza health status score.
8. **Time to viral clearance**, as assessed by difference in Percentage of Participants Positive by Influenza plaque assay and qPCR at each time-point (in each treatment group) The definition of the time to sustained cessation of infectious virus detection is the time

between the start of treatment and when virus titer remained below the detection limit on all subsequent sampling time points.

9. Measure treatment-emergent variants of neuraminidase and polymerase known to confer antiviral resistance to oseltamivir in each arm by direct next-generation sequencing symptoms [Time Frame: From Day 1 pre-treatment up to Day 30]

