3. STUDY DESIGN

3.1 DESCRIPTION OF THE STUDY

This is a randomized double-blind placebo-controlled pilot study of the efficacy and safety of baloxavir in combination with oseltamivir (SOC) for the treatment of influenza in allogeneic stem cell transplant patients.

30 SCT recipients with influenza will take part in the study. Participants will be randomly assigned (1:1) to either baloxavir + oseltamivir or baloxavir-matched placebo +oseltamivir. Randomization will be performed by research pharmacy using an interactive web randomizer. Before randomization, patients will be stratified by hospitalization status (yes or no), influenza type A (yes or no).

Patients in the baloxavir combination arm will receive weight-adjusted baloxavir (40 mg for patients weighing <80 kg and 80 mg for those weighing \geq 80 kg) at baseline and at day 4 and day 7. They will also receive oseltamivir 75 mg twice daily for 10 days.

Patients in the baloxavir-matched placebo + oseltamivir arm will receive baloxavir-matched placebo at baseline and at day 4 and day 7 and oseltamivir 75 mg twice daily for 10 days.

Nasopharyngeal swabs will be collected on days 1 (at diagnosis, pre-meds), 2, (optional visit), 4, 7 and 10 for viral quantitation and viral sequencing. Influenza virus polymerase and neuraminidase sequencing will be also performed in all patients. Patients will have follow-up visits day 15 (+/- 2 days) and day 30 (+/- 2 days, EOT). Patients who will not clear the virus by day 10 will perform additional NP swabs at these visits.

Paracetamol (acetaminophen; maximum 3000 mg per day) or NSAIDS can be given for severe discomfort or fever. No other antiviral drugs for the treatment of influenza, will be permitted, except antibiotics for the treatment of suspected bacterial infections.

For the first 10 days, patients will receive a daily call from one member of the study team to review symptoms and severity scale.

To assess the **time to improvement of individual influenza symptoms** (with modification for preexisting symptoms), participants will be given a diary to self-assess the severity of seven influenza-associated symptoms on a four-point scale. To evaluate patient-reported **time to return to pre-illness health status**, patients will also rate **daily the interference of influenza symptoms in daily activities** on a 5-point severity scale.

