4.2 SAMPLE COLLECTION AND PROCESSING

4.2.1 NASOPHARYNGEAL SAMPLING AND VIROLOGICAL ASSAYS

Two nasopharyngeal swabs will be collected at each visit and put immediately into viral transport medium and frozen. Pharyngeal swabs will be collected when if it is not possible to collect nasopharyngeal swabs. At the end of the clinical study period, samples will be used for viral sequencing and virological assessment.

Viral RNA in pre- and last post-treatment swab samples will be extracted using conventional RNA extraction kit without virus amplification and used for viral RNA quantification by q-PCR and for viral sequencing. Swabs will also be used to calculate viral titers by plaque assays on MDCK cells.

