Appendix 1 - Study Flowchart

Day(s)	D1	D2^a	D3	D4	D5	D6	D7	D8	D9	D10	D11 – D14	D15^b	EOS D30^{b,c}	Unsched Visit
On-site study visit	x	(x)		x			x			x		x	x	
Phone Visit			x	x		x	x		x	x				
Screening	x													
Informed consent and assent	x													
Inclusion/Exclusion criteria	x													
Randomization^d	x													
Demographics	x													
Medical history	x													
Concomitant medication monitoring	x			x			x			x		x	x	x
Physical examination^e	x ^e	x		x			x			x		x ^f	x ^f	x ^g
Body weight	x											x ^f		
Vital sign measurements^h	x											x ^f	x ^f	x ^g
Presence or absence of respiratory supportⁱ	x	x		x			x			x		x ^f	x ^f	x ^g
Blood hematology and chemistry^j	x			x ^f			x			x		x ^f	x ^f	x ^g
Blood liver chemistry^k	x			x			x			x		x ^f	x ^f	
Blood for exploratory biomarkers	x	x		x			x			x		x	x	
NP swab^l	x	x		x			x			x		x	x	x ^a
Chest X-ray/CT Scan^m	x													

Day(s)	D1	D2 ^a	D3	D4	D5	D6	D7	D8	D9	D10	D11 – D14	D15 ^b	EOS D30 ^{b,c}	Unsched Visit
On-site study visit	x	(x)		x			x			x		x	x	
Phone Visit		x	x		x	x		x	x					
Pregnancy test ⁿ	x													
Adverse events		x		x			x			x		x	x	x
Patient self assessment ^o	x	x	x	x	x	x	x	x	x	x	x	x	x	x
Xofluza/Placebo ^p	x			x			x							
NAI SOC (Oseltamivir) ^q	x	x	x	x	x	x	x	x	x	x				

CT = computed tomography; D = day; EOS = end of study; Hosp = Hospitalized; NAI = neuraminidase inhibitor; Random = Randomization; RIDT = Rapid Influenza Diagnostic Test; RT-PCR = reverse transcription polymerase chain reaction; SOC = standard-of-care; Unsched = Unscheduled; V = visit; VHP = Voluntary Harmonization Procedure.

- a. Optional visit
- b. A visit window of ± 2 days applicable.
- c. The EOS visit should occur approximately 20 days after the last dose of study drug.
- d. Randomization should occur as soon as possible, after screening and informed consent.
- e. A complete physical examination should be conducted at screening. At post baseline visits and as clinically indicated, limited, symptom directed physical examinations should be performed.
- f. Clinical procedures may be undertaken at investigator's discretion if symptoms and signs persist beyond the treatment period or if viral shedding is detected beyond Day 10.

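### The protocol contradicts itself on swabs after day 10; if Section 3.1 is followed, a single negative on day 10 counts as sustained viral clearance

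*Combined protocol and SAP*

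**What the plan says.** **Endpoint.** Section 2.1, secondary endpoint 8, is headed as a time to viral clearance, yet it is to be judged "as assessed by difference in Percentage of Participants Positive by Influenza plaque assay and qPCR at each time-point". It then defines sustained cessation of infectious virus as the time from start of treatment to when "virus titer remained below the detection limit on all subsequent sampling time points".

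**Sampling.** Three places give the swab schedule:
- Section 3.1 covers everyone through day 10: "Nasopharyngeal swabs will be collected on days 1 (at diagnosis, pre-meds), 2, (optional visit), 4, 7 and 10". All patients have visits on days 15 and 30, but of swabs it says: "Patients who will not clear the virus by day 10 will perform additional NP swabs at these visits".
- Section 4.2.1 has no such condition: "Two nasopharyngeal swabs will be collected at each visit".
- Appendix 1 marks the NP swab row on D1, D2, D4, D7, D10, D15 and D30. Neighbouring rows, such as physical examination and hematology, carry footnote f on D15 and D30. That footnote makes procedures discretionary when symptoms persist or "if viral shedding is detected beyond Day 10". The swab row does not carry it.

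**Assays.** Swabs are frozen, and Section 4.2.1 says: "At the end of the clinical study period, samples will be used for viral sequencing and virological assessment". For RNA quantification it names only the swab before treatment and the final one after it. Appendix 1, footnote l, specifies RT-PCR at screening only.

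**Analysis.** The Statistical Considerations give Kaplan-Meier estimates and a generalized Wilcoxon test for time to clearance. No confirmation or censoring rule is given for it, although Section 4.5.7 gives a censoring rule for symptom improvement.

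**The concern.** A definition that needs all later samples to be negative means something only if the later samples are fixed in advance. Under Section 3.1 they are not: whether a patient is swabbed after day 10 depends on the day-10 result, which is part of the outcome being measured. A patient who turns negative on day 10 would have no later sample that could contradict it. A patient still positive on day 10 would face two more.

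Study treatment ends on day 10, so days 15 and 30 are the only looks at virus off treatment. Under 3.1 any return of virus in a patient judged cleared goes unrecorded. The same missing swabs would remove late material from endpoint 9, which covers treatment-emergent variants up to day 30.

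The 3.1 condition also cannot be applied as written. Someone must know on day 10 who has cleared, but the study assays are run later and no day-10 test is named. The plan does not say whether PCR or titer decides.

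Finally, endpoint 8 combines two quantities, a time to event and a proportion positive per visit. They need separate analyses.

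**Working it through.** The plan states no figure for this endpoint, so there is none to reproduce. The check counts the samples that the definition requires under each schedule.

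**Inputs**
- Swab days under 3.1 for a patient negative on day 10: 4, 7, 10 (day 1 is baseline; day 2 is optional and left out).
- Swab days under 3.1 for a patient positive on day 10: 4, 7, 10, 15, 30.
- Swab days under 4.2.1 and Appendix 1 for every patient: 4, 7, 10, 15, 30.

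**Formula.** If *f* is the first negative visit of an unbroken negative run, the number of negatives needed is the number of scheduled swab days at or after *f*.

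| First negative on | Needed under 3.1 | Needed under 4.2.1 and Appendix 1 |
|---|---|---|
| Day 4 | 3 (days 4, 7, 10) | 5 (days 4, 7, 10, 15, 30) |
| Day 7 | 2 (days 7, 10) | 4 (days 7, 10, 15, 30) |
| Day 10 | 1 (day 10) | 3 (days 10, 15, 30) |
| Day 15 | 2 (days 15, 30) | 2 (days 15, 30) |
| Day 30 | 1 (day 30) | 1 (day 30) |

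**Reading the table**
1. Under 3.1 the requirement falls to one negative at day 10 and rises again to two at day 15. Clearing on day 10 is easier to establish than clearing on day 15, purely because of who is sampled.
2. The single-negative problem is confined to patients first negative on day 10. Those first negative on day 4 or 7 have three or two negatives, but under 3.1 they too are not observed after day 10.
3. Under Appendix 1 the requirement falls steadily, and virus present on day 15 or 30 can be detected in anyone. A single negative then suffices only for a patient first negative on day 30, so a rule for the last sample is needed under either schedule.
4. The 4.2.1 wording on RNA, read literally, is also affected. If the final swab is day 10 for some patients and day 30 for others, the sample quantified differs by outcome, and the intermediate visits that endpoint 8 needs by PCR are not covered at all.

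**The case against.** The strongest reply is that the protocol already schedules what is needed. Section 4.2.1 and Appendix 1 both call for swabs at the follow-up visits, and the missing footnote f on the swab row suggests that no condition was intended. On that reading the sentence in 3.1 is loose drafting and no data are lost. This stands to the extent that the defect is a contradiction between sections, and the consequences above follow only if 3.1 is the section followed. It does not remove the need to act, because nothing says which section prevails and a swab not taken cannot be recovered.

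It is also fair that this is the eighth of ten secondary endpoints in a 30-patient pilot. The Statistical Considerations call all between-arm comparisons exploratory, and the co-primary endpoints stop at day 10. The assay matters too: if PCR decides who has cleared, patients who are titer-negative but PCR-positive on day 10 would still be swabbed, and the gap for the titer definition is narrower.

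A reader might go further and infer that the design favours the combination arm, since an arm with more day-10 negatives would collect more unconfirmed clearances. The documents do not support that. The only viral-load figures in the sample-size text (6.5 log10 at baseline, SD 3, a fall of at least 3) are RNA values, while the definition uses infectious titer. No titer distribution, detection limit or rate of transient negatives is given. A calculation from all day-10 negatives would also count patients first negative on day 4 or 7, who are not in the single-negative group. Nor do the documents describe return of virus after clearance as an established problem here; they describe protracted shedding and emergence of resistance.

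**Conclusion.** The point holds as an internal contradiction with a conditional consequence. Sections 3.1, 4.2.1 and Appendix 1 disagree on who is swabbed on days 15 and 30. If 3.1 is followed, sampling for endpoint 8 depends on the outcome, a patient first negative on day 10 meets the definition with one sample, and later return of virus in patients judged cleared is not seen. If 4.2.1 and Appendix 1 are followed, those consequences do not arise.

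Under either reading three gaps remain: no assay is named for judging clearance at day 10, no rule covers a negative that is only the last sample, and one endpoint holds two measures.

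The size that can be stated is the count of required negatives: 3, 2 and 1 against 5, 4 and 3 for first clearance on days 4, 7 and 10, leaving out the optional day-2 swab. The size and direction of any between-arm bias cannot be derived from the documents. The effect is on interpretation of a secondary, exploratory comparison and not on the sample size or the co-primary endpoints. It should be corrected, because the correction is cheap and the missing samples would be irrecoverable.

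**What to change.** 1. Amend Section 3.1 to agree with 4.2.1 and Appendix 1: NP swabs on days 15 and 30 for every patient, whatever the day-10 result. This also removes the need for a day-10 test of clearance to decide who is sampled.
2. Define time to sustained clearance by plaque titer as the first negative visit with all later scheduled swabs negative. Analyse PCR separately under the same rule.
3. Censor patients whose only negative is their last available sample. State the censoring date, and how deaths and missed swabs are handled.
4. List percentage positive by visit, for each assay, as its own endpoint.
5. Reconcile the 4.2.1 wording on which swabs undergo RNA quantification with the visits that are to be analysed.

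The cost is mainly wording. The downside is the assay cost and mild discomfort of up to two swabbing visits for patients who have cleared, at visits they already attend and where Appendix 1 already lists the swab.

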Although it was shown that baloxavir is effective against oseltamivir--resistant influenza strains *in vitro* (Taniguchi *et al* 2019), and it was effective in treating influenza in the immunocompromised mouse model (Fukao *et al* 2019), no randomized--controlled trials are available on the use of baloxavir in SCT recipients or in other immunocompromised patients. In a pilot study, we administered baloxavir to 5 SCT recipients who were still symptomatic and shedding influenza after treatment with oseltamivir. Two of these patients had the codon variant H275Y, that is known to confer resistance to oseltamivir. We found that after one or two administrations of baloxavir, the patients could clear the virus and improve the influenza symptoms. One of the patients developed the I38T variant in the PA subunit of the IAV polymerase. High rates of the I38X PA variant have emerged during baloxavir treatment in clinical trials, and it has been associated with resistance to the drug (Hayden *et al* 2018). Despite the limitations of a small number of patients and lack of control group, our preliminary data (Salvatore *et al* 2020) suggest that baloxavir may be a useful treatment option for infections with influenza SCT patients, although the low barrier to resistance and the potential for transmissibility of baloxavir-resistant influenza virus raises concern.

Combination treatment with baloxavir and oseltamivir *in vitro* and in mice produced synergistic responses against influenza virus infections. In this model, a suboptimal dose of baloxavir marboxil (0.5 mg/kg twice daily) in combination with oseltamivir phosphate provided additional efficacy compared with monotherapy in terms of virus-induced mortality, elevation of cytokine/chemokine levels and pathological changes in the lung suggesting that treating humans with the combination may be beneficial (Fukao *et al* 2019 b). Despite this treatment option may be more effective in clearing influenza virus infection and decrease the rate of emergence of resistant influenza in immunocompromised hosts no data about combination therapy in human are currently available. This study was therefore designed with the primary objective to compare the efficacy of the combination therapy of baloxavir with oseltamivir with oseltamivir plus placebo.

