In the Flagstone study, the incidence of adverse events was comparable between the two treatment arms regardless of the number of Xofluza or placebo doses that were received. One serious adverse event (orthostatic hypotension) in the placebo arm was considered treatment related.

Table 4: FLAGSTONE – Incidence of Adverse Events*

	Baloxavir + SoC NAI (n=239)	Placebo + SoC NAI (n=124)	All Patients (n=363)
Patients with ≥ 1 AE	108 (45.2%)	62 (50.0%)	170 (46.8%)
Total number of AEs	279	180	459
Deaths	4 (1.7%)	7 (5.6%)	11 (3.0%)
Patients withdrawn from treatment due to AE	3 (1.3%)	4 (3.2%)	7 (1.9%)
Serious AEs, patients (%)	29 (12.1%)	19 (15.3%)	48 (13.2%)
Treatment-related serious AEs, patients (%)	0	1 (0.8%)	1 (0.3%)
Treatment-related AEs, patients (%)	8 (3.3%)	8 (6.5%)	16 (4.4%)

Notes: *Safety population. Investigator text for AEs encoded using the MedDRA version 23.0. Related AEs are related to study drug only.

Abbreviations: AE(s)=adverse event(s); MedDRA=Medical Dictionary for Regulatory Activities; NAI=neuraminidase inhibitor; SoC=standard of care

Our study will randomize SCT recipients with influenza to receive baloxavir + oseltamivir (SOC) or oseltamivir + baloxavir matching placebo and assess if the combination of baloxavir with oseltamivir will translate in a more rapid decrease of viral load and faster symptoms resolutions when compared to oseltamivir alone. It will also test if combination therapy may lower the incidence of drug-resistant influenza variants.

In summary, there is a strong rationale and a positive benefit-risk assessment for studying Xofluza combination therapy in SCT recipients. Safety and efficacy results suggest that Xofluza has an acceptable clinical safety profile and could benefit in immunocompromised patients. Given the poor treatment responses to single therapy in SCT, this population is considered appropriate for trials of combination therapy. The benefit-risk ratio for Xofluza in combination with oseltamivir is expected to be acceptable in this setting.

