For secondary viral loads related endpoints, summary statistics in terms of mean, standard deviation, median and range will be calculated for each arm at each time points among patients with relevant measurements. Longitudinal analyses using mixed effects repeated measures will be used to model the mean viral loads overall time. Contrasts of interest including between arm differences will be explored using simultaneous tests of general linear hypotheses. If normality is a concern, log-transformed and standardized viral load data will be used. Longitudinal analysis will be carried out among patients with at least one relevant viral load measurement. Kaplan-Meier estimates will be generated for time to events endpoints such as time to Improvement of Individual Influenza Symptoms, the time to viral clearance and time to return to preinfluenza health status for each study arm. Between study arm difference in these endpoints will be explored using the generalized Wilcoxon test.

Categorical data such as the occurrence of treatment-emergent variants of neuraminidase and polymerase by direct next-generation sequencing and AE's will be summarized in terms of counts and proportions separately for each arm.

Between arm difference in the categorical variable will be explored using Fisher's exact test. The study is likely will not have adequate power to detect between arm differences and all the between arms comparisons are considered exploratory. Summary statistics generated for study endpoints for each arm will provide useful information for planning future studies.

The power calculations were performed using PASS 15 Power Analysis and Sample Size Software (2017). NCSS, LLC. Kaysville, Utah, USA, ncss.com/software/pass. All comparisons will be two-tailed, with a significance level at 0.05 and 95% confidence intervals will also be reported. All analyses will be performed in SAS Version 9.4 (2019), SAS Institute, Inc., Cary, NC; and R Version 4.0.4 (2021).

Note: The statistical considerations section was written by [name], MS, and revised by [name], in the Division of Biostatistics, Department of Population Health Sciences, Weill Cornell Medicine.

Influenza sequence analysis will be performed by [name], Director of Systems Genomics Section at the Laboratory of Parasitic Diseases of NIAID/NIH and expert in Influenza evolution.

No interim analysis is planned for this study

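### Secondary endpoint 9 counts only variants conferring resistance to oseltamivir, so emergent baloxavir resistance (PA I38X) is not an event, contrary to the stated aim and the analysis text

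*Combined protocol and SAP*

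**What the plan says.** Section 2.1, secondary endpoint 9: "Measure treatment-emergent variants of neuraminidase and polymerase known to confer antiviral resistance to oseltamivir in each arm by direct next-generation sequencing". The genes named are neuraminidase and polymerase; the only drug named is oseltamivir.

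Section 1.3 distinguishes resistance by drug. In the five-patient pilot, "Two of these patients had the codon variant H275Y, that is known to confer resistance to oseltamivir". For baloxavir, "One of the patients developed the I38T variant in the PA subunit of the IAV polymerase", and more generally "High rates of the I38X PA variant have emerged during baloxavir treatment in clinical trials, and it has been associated with resistance to the drug". It adds that "the low barrier to resistance and the potential for transmissibility of baloxavir-resistant influenza virus raises concern". Later in the same section the aim is stated without limiting it to one drug: "It will also test if combination therapy may lower the incidence of drug-resistant influenza variants".

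Section 3.1 provides the data: "Influenza virus polymerase and neuraminidase sequencing will be also performed in all patients".

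Statistical Considerations lists, among categorical data to be summarised by arm as counts and proportions, the "occurrence of treatment-emergent variants of neuraminidase and polymerase by direct next-generation sequencing". It attaches no drug and gives no list of substitutions. Between-arm differences in categorical variables are explored with Fisher's exact test, and all between-arm comparisons are called exploratory.

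**The concern.** Both arms receive oseltamivir; only the combination arm receives baloxavir. An endpoint restricted to oseltamivir resistance counts resistance to the shared drug and leaves out resistance to the added one. If adding baloxavir reduced neuraminidase variants but selected PA variants, the endpoint would record the first effect and not the second. That omission can only favour the combination arm.

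The protocol itself names baloxavir resistance, and its possible transmission, as a reason for caution, and the study sets out to learn whether the combination lowers resistance. A pilot whose per-arm summaries are meant to inform later studies should not leave the definition of a resistance event open until the sequences are in hand.

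**Working it through.** The plan states no rate, power or sample size for endpoint 9, so there is no figure to reproduce. The check is a comparison of the texts, followed by an illustration.

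**1. Would a treatment-emergent PA I38X variant count?**

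| Place | What is covered | PA I38X counted? |
|---|---|---|
| Section 1.3, aim | Drug-resistant variants, no drug named | Yes |
| Section 2.1, endpoint 9 | Neuraminidase and polymerase variants conferring oseltamivir resistance | No: the protocol links I38X to baloxavir only |
| Statistical Considerations | Neuraminidase and polymerase variants, no drug named | Yes on its face, but it does not redefine the endpoint |

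The other secondary endpoints cover viral load (1 to 4), symptoms (5), complications (6), health status (7), viral clearance (8) and adverse events (10). The exploratory endpoint is cell-free DNA. None covers baloxavir resistance.

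Endpoint 9 also sits awkwardly with itself. It names polymerase, yet every polymerase variant discussed in Section 1.3 relates to baloxavir, and the only oseltamivir variant named there is H275Y.

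**2. How the definition changes the result (hypothetical counts, 15 evaluable patients per arm).** Suppose 3 control patients have neuraminidase variants. Suppose no combination patient does, but 3 combination patients have PA I38X.

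- Endpoint 9 as written: 3/15 control against 0/15 combination.
- Resistance to either drug: 3/15 against 3/15.

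The apparent advantage disappears with no change in the sequences. For 3/15 against 0/15 the two-sided Fisher p is 2 × C(15,3)/C(30,3) = 2 × 455/4060 = 0.22. What would mislead is therefore the descriptive picture, not a significance claim.

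**3. Could the omitted category be non-empty?** The documents give no rate for combination therapy, so the rates below are assumptions. The chance of at least one PA variant among 15 patients is 1 − (1 − p)^15:

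| Assumed p | Chance of at least one |
|---|---|
| 5% | 1 − 0.95^15 = 54% |
| 10% | 1 − 0.90^15 = 79% |
| 20% | 1 − 0.80^15 = 96% |

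This shows only that uncounted events are plausible over that range. It does not estimate their number.

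**4. What the pilot supports.** One of 5 is 20%, with an exact 95% interval of about 0.5% to 72%.

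**The case against.** The strongest reply is that this is a slip of drafting. Naming polymerase makes little sense unless baloxavir resistance was intended, the aim in Section 1.3 is general, and the analysis text carries no oseltamivir limit. An analyst following Statistical Considerations alone would tabulate PA variants. This stands as an account of how the wording probably arose. It does not settle which text governs: the analysis section supplies neither a definition nor a list of substitutions to replace the endpoint's.

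It is also fair that all arm comparisons are exploratory and likely underpowered, that no decision rests on endpoint 9, and that Section 1.3 raises neuraminidase-inhibitor resistance as well, so baloxavir resistance is not the only resistance risk in view. These points limit the consequence but leave the gap in place.

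A reader might infer three stronger things that the documents do not support:

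- **That baloxavir resistance will go unmeasured.** It will not: Section 3.1 sequences polymerase in all patients. The gap is in the definition, not the data.
- **That the plan merges neuraminidase and PA variants into one composite test.** Statistical Considerations specifies no composite; tabulating by gene fits its wording equally well.
- **That the pilot rate predicts how many combination patients will be missed.** Those five patients had no controls and received baloxavir after oseltamivir, while still shedding virus. Carrying their rate over to up-front combination therapy would set aside the hypothesis that the combination lowers resistance.

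**Conclusion.** The concern holds as a conflict of definition. Endpoint 9 taken literally excludes the PA variants that the protocol links to baloxavir; the stated aim and the analysis text do not. Three sections therefore allow different event counts from the same sequences, and the literal one can flatter the combination arm.

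The conclusion rests on two readings: that I38X is not also classed as an oseltamivir-resistance variant (the protocol links it only to baloxavir), and that an endpoint definition governs unless the analysis section replaces it. The number of events affected cannot be stated, because the documents give no usable rate under combination therapy. The consequence is confined to an exploratory secondary comparison. It is still worth correcting before unblinding, since choosing among the three readings afterwards would be a post hoc decision.

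**What to change.** Redefine secondary endpoint 9 as treatment-emergent variants associated with resistance to oseltamivir (neuraminidase, for example H275Y) or to baloxavir (PA, for example I38X). Report by arm:

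- the number and proportion with oseltamivir-resistance variants;
- the number and proportion with baloxavir-resistance variants;
- the number and proportion with resistance to either drug.

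The either-drug count should be read beside the two separate counts, because one arm is exposed to two drugs and the other to one. Use the same definition in the aim in Section 1.3, in Section 2.1 and in Statistical Considerations. The comparisons can stay exploratory.

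The cost is an amendment of wording. Both genes are already sequenced in all patients (Section 3.1), and Section 4.2.1 provides for sequencing of pre-treatment and last post-treatment swabs, so no further sampling or assay is required.
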